#### 4. Study Procedures

##### **Primary Objective: To conduct a pilot EMAI study with smartphones in Rakai, Uganda.**

**Study design.** This pilot study will be nested within the Rakai Community Cohort Study (RCCS, WIRB #20031318), an ongoing, population-based, prospective, observational study which surveys Rakai District communities in Uganda every ~12-18 months.

**Study setting and population.** Rakai District (~2200 km^2) is a mostly rural district (population~400,000) in Uganda bordered by Tanzania and Lake Victoria. RHSP has been conducting community-based research in Rakai since 1988 including large, prospective health behavior studies. RHSP survey results of demographic and behavioral characteristics are similar to those reported for southwestern Uganda in Demographic and Health Surveys, suggesting that despite long-term surveillance and health education, the population is typical of rural/semi-rural Uganda.

**Rakai Community Cohort Study (RCCS):** RHSP's ongoing 54 community (n~20,000) longitudinal HIV surveillance study provides >20 years of data on HIV prevalence/incidence, health behaviors, sexual networks, and mobility/migration in Rakai District, Uganda.

**Eligibility.** We will aim to recruit 120 total adults (age  $\geq 18$  years) from current, literate RCCS study participants. We will purposely recruit a sample that has a broad range of participant characteristics in our study to optimize diversity of responses and increase study generalizability. Specific variables for which we will target sampling include: gender (~50% female), age (at least 20% among age groups 18-25, 26-35, >50), and occupation (at least 20% traders and farmers).

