*Follow-up (Days 31-90, Randomized Evaluation).* After completing the Day 30 questionnaire, participants will be randomized using a computerized random number generator, in a 1:1 ratio, to either continue receiving assessment questions only (control arm) or to also begin receiving intervention messages (intervention arm). After reaching 60 and 90 days of follow-up, participants will return to the study office to complete a brief questionnaire on behaviors and experiences with the phone. After 90 days of follow-up participants will also return their phones to study staff.

*Logistics.* Phones will be preloaded with airtime. If additional airtime is needed, participants can “beep” (call and hang up, no cost to caller) study staff to transfer airtime to phones using locally available services.

*Smartphone loss/theft.* Installed software will allow for GPS-locating of lost/stolen phones and can remotely wipe data on phones as needed. Participants will be notified that they will not be eligible for their incentives if they lose or have their phones stolen. These participants will remain in all study analyses (intention-to-treat) but will not receive a second phone.

*Smartphone malfunction.* Participants will be asked to communicate with study staff either in-person or remotely should their smartphone malfunction. Malfunctioning phones will be returned to study staff if necessary. IT support will be available to troubleshoot phones during regular business hours throughout the study. Study staff will record all instances of malfunctioning phones as part of process evaluations.

**EMAI Application.** The EMAI application for this study will be programmed following user centered design principles on the *emocha* platform.

*Prompts.* The EMAI application will send prompts (audible alert and text message asking them to complete a specific form, no specific health information revealed in prompts) to participants at 3 times: daily, random, weekly. Daily prompts will occur once a day at a scheduled time, a random prompt occurs once a day at an unscheduled time, and a weekly prompt occurs once a week at a scheduled time. The diversity of prompts allows for a range of response patterns. Participants will be allowed to respond to read form and respond to prompts only after entering a password.

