**Timeline for proposed study.**

Activity	Study Month→	1-2	3-4	5-6	6-7	7-8	9-10	11-12	13-14	15-16	17-18	19-20	21-22	23-24
Formative work on messaging														
mHealth EMAI Software Programming and Testing														
EMAI Recruitment and Implementation (90 days total per participant, follow-up periods will be asynchronous)														
Mixed Methods Evaluations														
Final Analyses and Dissemination														

- 5. **Inclusion/Exclusion Criteria**-See above.
- 6. **Drugs/ Substances/ Devices**-Not applicable.
- 7. **Study Statistics (for Primary Objective)**

**Sample Size/Power Calculations.** This is an exploratory study powered not to assess intervention efficacy but to provide preliminary estimates of effect. As an example, Table 3 shows power calculations for alcohol use based on different estimates of intervention impact. Prior data indicate that approximately 50% of the Rakai population uses alcohol on a weekly basis. If there is a 50% reduction in alcohol use following EMAI, the study will have 81.5% percent power to detect this difference.

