**Table 3: Power calculations.**

% Reduction In Behavior	Power
20	0.195
30	0.381
40	0.611
50	0.815

**Change in health behaviors following EMAI.** We hypothesize that EMAI results in improved health behaviors. We will use data on health behaviors obtained prior to the start of the randomized phase, Days 1-30, to characterize baseline behaviors for each participant. Changes in baseline behaviors will be assessed from 30-90 days relative to baseline in intervention and control arms. The relative change from baseline to follow-up (e.g. change in proportion of yes responses to daily alcohol use over Days 1-30 compared to Days 31-90), will be compared between intervention and controls arms using mixed effects models. Temporal trends in behaviors in each arm over the entire 90 day period also will be identified and characterized.

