### **Data and Safety Monitoring Plan**

The risks of this study are minimal compared to trials involving biomedical interventions or procedures. We have developed a data and safety monitoring plan in accordance with this lower level of risk. Primary responsibility for data and safety monitoring will be assumed by the principal investigator ([name]).

Data risks and monitoring: The primary data risks are inadequate quality of data collection, unacceptable intervention acceptance rates, data security, and unintended harm of health messaging. To address these risks, the principal investigator will review data quality and intervention acceptance rates on a quarterly basis. If risks are realized, investigators will consider stopping the study and/or taking appropriate steps to improve study quality and ensure adequate power. Electronic data security will be maintained with password protected computers accessible only to relevant study staff. Transcribed data will be secured in designated locked facilities at RHSP. Any data risk will be reported in a timely fashion to the appropriate IRBs. Any possible harm reported by participants will be immediately addressed by the PI and study team and reported to appropriate IRBs.

Safety risks and monitoring: The primary risks in this study are social harms related to loss of confidentiality and embarrassment and sensitivity related to discussions about sensitive topics such as health and sexual behaviors. To minimize these risks, we will perform informed consent and utilize a strong training curriculum that emphasizes strict confidentiality and protecting against inadvertent

Date: March 30, 2015

Principal Investigator: [name], MPH

Application Number: IRB00065934

disclosure. Additionally, we will ensure that training emphasizes caring, non-judgmental, and non-threatening approaches to the questioning, counseling, and teaching of participants. We will train study-related personnel to stop their tasks if the participant appears to be in distress and to contact higher-trained staff if distress is noted. Any breaches of confidentiality will be considered an adverse event and immediately reported to the principal investigator. Should any adverse event occur which may be related to study activities, an adverse event form will be completed by study staff and the event immediately reported to the principal investigator.

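### Does the protocol need to define adequate power, and state the method behind Table 3, before its monitoring clause can be applied?

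*Combined protocol and SAP*

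**What the plan says.** Section 7 (Sample Size/Power Calculations) first limits what the calculation is for: "This is an exploratory study powered not to assess intervention efficacy but to provide preliminary estimates of effect". It then introduces the table as an illustration, "As an example, Table 3 shows power calculations for alcohol use based on different estimates of intervention impact", takes a weekly alcohol use of about 50% from prior data, and ends with "If there is a 50% reduction in alcohol use following EMAI, the study will have 81.5% percent power to detect this difference". Table 3 has two columns, the percentage reduction (20, 30, 40, 50) and the power (0.195, 0.381, 0.611, 0.815).

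The numbers needed to read the table are in Section 4. Under Eligibility: "We will aim to recruit 120 total adults". Under Follow-up (Days 31-90), allocation is 1:1. On lost or stolen phones: "These participants will remain in all study analyses (intention-to-treat) but will not receive a second phone".

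The planned between-arm analysis, also in Section 7, is of a different kind from a single comparison of two proportions. The change from baseline to follow-up "will be compared between intervention and controls arms using mixed effects models".

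The Data and Safety Monitoring Plan lists four data risks: poor data collection, low acceptance of the intervention, data security, and harm from the messages. It says "the principal investigator will review data quality and intervention acceptance rates on a quarterly basis", and then: "If risks are realized, investigators will consider stopping the study and/or taking appropriate steps to improve study quality and ensure adequate power".

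**The concern.** Two things look wrong together. First, a reader cannot tell from Section 7 how the 81.5% was obtained. The test, alpha, sidedness, number analysed and loss assumption are all absent, and nothing says that the table's method differs from the mixed-effects comparison described directly after it.

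Second, the monitoring plan appears to put power to use in running the study. It speaks of ensuring adequate power in the same sentence as stopping, yet no section gives a target power, a reference effect or a minimum number analysed, and Section 7 disclaims power for efficacy. If power were a monitoring criterion, the person applying it would not know which row of Table 3 to protect. Under the 50% row there would be little room for loss. Under the 40% row or below, power is 0.611 or less even with every recruit analysed. Different readings could then lead to different actions on the same data.

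**Working it through.** **1. Reproduce Table 3.** Inputs: control proportion p1 = 0.50 (Section 7); p2 = 0.50 × (1 − r) for reductions r of 20, 30, 40 and 50% (Table 3), so 0.40, 0.35, 0.30 and 0.25; 120 recruits (Section 4, Eligibility) at 1:1 (Section 4, Follow-up Days 31-90), so n = 60 per arm. Assumed, because not stated: two-sided alpha of 0.05, pooled variance under the null, no continuity correction, no loss.

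With d = p1 − p2 and p̄ = (p1 + p2)/2:

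- SE0 = √[2 p̄(1 − p̄)/n]
- SE1 = √{[p1(1 − p1) + p2(1 − p2)]/n}
- Power = Φ[(d − 1.96 SE0)/SE1] + Φ[(−d − 1.96 SE0)/SE1]

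For r = 50%: d = 0.25 and p̄ = 0.375. SE0 = √(2 × 0.375 × 0.625/60) = 0.0884. SE1 = √[(0.25 + 0.1875)/60] = 0.0854. Then (0.25 − 1.96 × 0.0884)/0.0854 ≈ 0.90, and Φ = 0.816. The far tail is negligible here.

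| Reduction | Stated | Computed |
|---|---|---|
| 20% | 0.195 | 0.1950 |
| 30% | 0.381 | 0.3816 |
| 40% | 0.611 | 0.6111 |
| 50% | 0.815 | 0.8157 |

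Every row agrees within 0.001.

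**2. Could other methods have produced the table?** At 60 per arm, the 50% row is 0.890 one-sided, 0.759 with a continuity correction and 0.760 by Fisher's exact test; none of these fits. The two-sided arcsine (0.818) and unpooled (0.833) forms come within 0.02. One-sided 5% with a continuity correction at 53 to 54 per arm also comes within 0.02 across the rows. The pooled two-sided test with all 120 analysed is the closest match of those tried, and it uses the protocol's own sample size. The method is therefore inferred with good support, though not proved.

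**3. How much does the unstated loss assumption matter?** The documents give no attrition rate. By the same formula the 50% row is 0.809 at 59 per arm. If 10% or 20% of participants contributed nothing at all (assumed rates), it would be 0.773 at 54 per arm and 0.722 at 48. These figures would qualify a claim of efficacy power, which Section 7 does not make.

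**4. What does the monitoring sentence do?** Set out in order: the principal investigator reviews data quality and acceptance each quarter; if one of the listed risks has occurred, the investigators consider stopping or corrective steps; those steps are meant to improve quality and keep power adequate. The condition is the occurrence of a data risk. Neither loss alone nor low power for a small effect is on the list. Nobody is asked to compute power and compare it with a limit, so the sentence gives no instruction to act on any loss or to act from the outset.

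**5. Does it contradict Section 7?** It need not. Section 7 uses the word powered in connection with preliminary estimates of effect. Read the same way, adequate power in the monitoring plan means enough usable data for those estimates. That is loose wording, but it is consistent with the stated purpose.

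**The case for a change.** The best case for acting is that the omission is real and cheap to repair. A power table should state its test, alpha and number analysed. Losses are foreseeable: participants may return the phone and leave at any time, and they must come back at Day 30 before randomization, so fewer than 120 may be randomized. Keeping people with lost phones in the analysis does not say how their missing responses are handled. A discretionary clause still needs something to refer to. If 0.815 is taken as the level to keep, the number per arm is 60, 97, 176 or 403 for reductions of 50, 40, 30 or 20%, that is, 120 to 806 in total.

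The reporting point stands: those details are missing, and one phrase in the monitoring plan is imprecise. The consequences drawn from it do not stand. The range from 120 to 806 takes the power of one illustrative row and imposes it on the others as a target, which the protocol never does; Table 3 already shows the low power for smaller effects. The table is also not the power of the mixed-effects comparison. That power cannot be derived from the documents and could be higher or lower, so the difference in method shows no defect in the sample size.

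**Conclusion.** No change to the plan is needed. Table 3 is correct to within 0.001 on assumptions that a statistician would try first and that match the protocol's own 120 participants at 1:1. The missing test, alpha, sidedness and loss statement are gaps in the description of an example, in a pilot that disclaims power for efficacy. The monitoring sentence leaves a judgment to the investigators once a listed data risk has occurred; it contains no power threshold to define. Carrying out the protocol exactly as written would give the same data, the same analysis and the same conclusions as a version with the details added.

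This rests on two assumptions: that Table 3 came from the pooled two-sided 5% test, which the match supports but the documents do not state, and that adequate power in the monitoring plan carries no meaning beyond its sentence. The figures of 0.773 and 0.722 depend on assumed loss rates and support no action by themselves. The conclusion would be different if the protocol set a power target or tied stopping to one; it does neither.

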**Table 3: Power calculations.**

% Reduction In Behavior	Power
20	0.195
30	0.381
40	0.611
50	0.815

**Change in health behaviors following EMAI.** We hypothesize that EMAI results in improved health behaviors. We will use data on health behaviors obtained prior to the start of the randomized phase, Days 1-30, to characterize baseline behaviors for each participant. Changes in baseline behaviors will be assessed from 30-90 days relative to baseline in intervention and control arms. The relative change from baseline to follow-up (e.g. change in proportion of yes responses to daily alcohol use over Days 1-30 compared to Days 31-90), will be compared between intervention and controls arms using mixed effects models. Temporal trends in behaviors in each arm over the entire 90 day period also will be identified and characterized.

**Mobility patterns and health outcomes.** The extent to which individuals travel local and long distances is likely a significant predictor of health outcomes We will use EMAI data to characterize participants' mobility patterns and the associations between these patterns and health behaviors in intervention and control arms. All GPS data will be cleaned using standardized methods, with emphasis on identification in coordinate outliers and missing coordinate data. Individuals in each arm will be classified into 3 groups based on their mobility data: low mobility (limited local movement), high local mobility (frequent local movement only), and high long distance mobility (frequent local and longer distance travel or long distance travel only). Spatial travel kernels at daily, weekly, and monthly intervals will be estimated using maximum likelihood methods and GPS data fit to various statistical distributions. The best fit spatial kernels will be used to determine the extent of local and longer distance movement and to establish cutoffs for the appropriate categorization of mobility patterns, where individuals' primary residential location will serve as the anchor location from which distance of movements are measured. Mobility patterns will be correlated with participant demographics and self-report of behaviors obtained via the EMAI using random effects regression models for binary and ordinal outcomes in intervention and control arms. Data on mobility patterns and their association with health outcomes will be informative to health behavior programs and for a wide variety of modelling studies on infectious disease transmission, including HIV.

8. **Risks**

Date: March 30, 2015

Principal Investigator: [name], MPH

Application Number: IRB00065934

**Potential risks/harms.** Risks from this study include the loss of confidentiality in reporting potentially sensitive health information. Having a smartphone in their possession may also make participant targets for theft or exploitation. All smartphones will require an unlocking password and will be inaccessible without that password. Each participant and project personnel will be allocated a password to authenticate correspondence and prevent unauthorized parties from accessing information or providing false information. The health advice participants receive through the EMAI application may not be accurate, relevant, and may cause unintended harm. There is also risk of embarrassment, personal discomfort, and sensitivity to discussing and answering questions related to sexual behaviors and other sensitive subjects. Subjects may also become fatigued from interviews and meetings. The likelihood of these risks is small based upon previous RHSP studies and experiences.

**Protection against risks. Recruitment and informed consent:** Recruitment and informed consent: Participants provide written informed consent for RCCS, the parent study within which this study is nested. RCCS participants provide consent for recontact for other unspecified studies. Potential participants for this study will be approached by trained research staff. Staff will read, review, and discuss the study purpose, subject involvement, risks, potential benefits, and new consent forms specific to this study with potential subjects. All discussions and written material will be in the native language of the region (Luganda). All translations will be certified by a nationally recognized organization (Makerere University). If the participant agrees and is able to express a summary and understanding of the study, they will sign the consent form and be given a copy. Signed consent forms will be secured at the RHSP offices in Rakai.

Protection of confidentiality: *Research materials:* Materials will include the interviews, consent forms, and mobile phone logs of all activity conducted through the mHealth application. In order to preserve confidentiality, informed consent documents – which by definition include the participant's name - are retained in locked filing cabinets and secure store rooms, accessible only to senior investigators or designated staff. No personal identifiers will be attached to the questionnaire or samples. Electronic data sets and clinical readouts are downloaded into password protected computers, and individual identifiers are stripped. Names linked to study IDs are stored in a separate, password protected electronic file, on a computer and server accessible only to authorized senior personnel. All RHSP research staff have received extensive human subjects/research ethics training, including the need for complete confidentiality. Participant entered EMAI data will be encrypted at all times, be it on the phone, with data transfer, or sitting on the server. The application and server access will be password protected. If a phone is lost or stolen, we will have the ability to remotely wipe the phone of all data and render it inoperable. All interviews will be conducted in private or, if appropriate, as a focus group. If a breach of confidentiality occurs, we will report to the appropriate IRBs according to NIH guidelines. The principal investigator will discuss any breaches of confidentiality and intervene as necessary to decrease the risk of future breaches.

Avoidance of social harm: We will counsel participants on the need to be discrete with their smartphones to avoid risk of being targeted for theft or exploitation. We will attempt to use locally available smartphones to minimize the novelty of participants using these devices. We will teach participants to immediately contact study staff if they have any negative experiences and they will be able to return the phones and quit the study at any time.

Date: March 30, 2015  
Principal Investigator: [name], MPH  
Application Number: IRB00065934

Protection from discomfort, embarrassment, and fatigue: To mitigate these concerns, the following procedures will be implemented: (i) Training of research staff will emphasize caring, non-judgmental, and non-threatening approaches to the questioning, counseling, and teaching of patients; (ii) Research staff will be trained to stop their tasks if the patient appears to be in distress and to contact higher-trained staff if any distress is noted; (iii) Participants will be informed that they have the right to withdraw from the study at any time without any adverse consequences.

Protection from unintended consequences: Participants may encounter a variety of complex and unanticipated situations in the field once they begin this pilot study. Study team members will be available at all times via mobile phone for any situations which may arise. Participants may be confused by health messaging or have unintended harm from health messaging this is incorrect or inappropriate. RHSP health facilities are and will continue to be available to all participants free of charge and participants will be instructed to seek the advice of a health provider should there be any confusion or health concern. Overall, the EMAI is more likely to provide benefit rather than unintended harm. Additionally, our current and published experiences with EMAI have not found significant instances of harm.

mHealth-Specific Concerns: Special mention is made here regarding the ethical issues around EMAI, particularly the “tracking” aspects and use of geolocated data which will be linked to sensitive behaviors. In addition to full informed consent, the application, phones, and server will use rigorous security methods (passwords, encryption, remote data wiping, user controls, etc.) to help protect subjects. All geolocation data will be presented in anonymized and de-identified fashions (e.g. blurring specific locations to prevent identification). In the secondary objectives, we will specifically ask participants for their perspectives on the ethical issues of EMAI.

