# Mobile Behavioral Ecological Momentary Assessment and Intervention in Rakai, Uganda: A Pilot Study

## 1. Abstract

Ecological Momentary Assessment and Intervention (EMAI) is an emerging technique for gathering richer and more relevant data through repeated, longitudinal sampling of participants in their natural setting in order to deliver real-time interventions. Challenges with instilling healthy behaviors are well documented. These challenges are magnified in low and middle income countries (LMICs) where significant social and structural barriers to care often exist. The rapid emergence of mHealth (mobile technologies for health), including growing access to low-cost smartphones, now allows for unprecedented advancements in and novel research on mHealth applications in LMICs. We therefore propose a pilot EMAI study of health behavior in Rakai, Uganda.

This study aims to demonstrate that it is feasible and acceptable to use smartphones in a LMIC to collect near real-time, geolocated behavioral information and to send tailored health messages based upon this data. This proposal will provide unique insights into the geospatial/temporal epidemiology of health behaviors, generate preliminary estimates of intervention impact, and establish an evidence-base for future large-scale, randomized EMAI mHealth trials. This study will be nested within the Rakai Health Sciences Program's (RHSP) ongoing Rakai Community Cohort Study (RCCS).

Our main study objective is to conduct a pilot EMAI study among current RCCS study participants. Participants will be given a smartphone with an application that will collect GPS-based geolocations and ask assessment questions (e.g. diet/alcohol, smoking, and sexual behaviors). Using participants' responses, the application can deliver tailored intervention health messaging to participants using pre-programmed algorithms. During Days 1-30 of follow-up, all participants will receive assessment questions only to establish baseline behaviors. During Days 31-90, participants will be randomized to either continuing with assessment questions only (control arm) or to also begin receiving intervention messaging (intervention arm). The randomized design will allow for calculation of an estimate of EMAI effect on diet/alcohol, smoking, and sexual behaviors which will be used to design future, large-scale randomized controlled trials of EMAI.

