**Table 1: EMA application sample questions.**

Forms	Behavior Domains	Questions
Daily	Smoking, Diet/Alcohol Use, Sexual Activity	Did you smoke today/this week? (yes/no) If so, how many items did you smoke today? (#); Did you eat any vegetables today/this week? (yes/no); Did you use any alcohol today/this week? (yes/no); Did you have any sex with anyone who was not your marital or long-term partner today/this week? (yes/no) If so, did you use condoms? (yes/no)
Random		
Weekly		
Event-contingent	Smoking, Diet/Alcohol Use, Sexual Activity	Checklist Format: Within the past hour, I smoked, ate vegetables, drank alcohol and/or had sex with someone who was not my marital or long-term partner.

In response to data entered by participants, the EMAI application will be programmed with algorithms to provide real-time feedback, i.e. EMI, through tailored health text messages. Only patients randomized to the EMI arm will receive these messages. We will use general health as well as behavior-specific messaging. Examples are shown in Table 2.

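### Section 7 compares arms on a relative change from baseline with no effect scale and no baseline covariate or constraint; adjusting for the Days 1-30 proportion is more precise than simple change and nearly free

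*Combined protocol and SAP*

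**What the plan says.** The only description of the randomized comparison is the paragraph on change in health behaviors in Section 7. It states that "Changes in baseline behaviors will be assessed from 30-90 days relative to baseline in intervention and control arms". The measure is "The relative change from baseline to follow-up (e.g. change in proportion of yes responses to daily alcohol use", Days 1-30 against Days 31-90, which "will be compared between intervention and controls arms using mixed effects models". The paragraph does not say:

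- whether the change is a ratio or a difference, or is taken per person or per arm;
- which link function and random effects the model has;
- whether the Days 1-30 proportion enters as a covariate, or the arms are constrained to a common baseline mean;
- what happens to a participant with no baseline yes.

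The underlying data are repeated yes/no answers, for example "Did you use any alcohol today/this week? (yes/no" in Table 1 (Section 4). Table 3 expresses effects as a percentage "Reduction In Behavior" and rests on this input: "Prior data indicate that approximately 50% of the Rakai population uses alcohol on a weekly basis".

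On purpose, Section 7 says: "This is an exploratory study powered not to assess intervention efficacy but to provide preliminary estimates of effect". The Abstract says the design will give "an estimate of EMAI effect on diet/alcohol, smoking, and sexual behaviors which will be used to design future, large-scale randomized controlled trials of EMAI".

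**The concern.** A relative change and a change in proportion are different quantities, and one sentence names both. The main product of this pilot is an effect estimate to be carried into later trials, so its definition and its precision both matter.

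Two of the possible readings have a cost. Simple change fixes the coefficient on baseline at 1, whereas adjustment estimates it and so usually gives a tighter interval from the same data. A per-person ratio cannot be computed when the baseline is zero, and it is unstable when the baseline is small. Eligibility in Section 4 does not require drinking, smoking or sex outside the main partnership, so zero baselines will be common.

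**Working it through.** **Inputs from the protocol.** 120 participants randomized 1:1, so 60 per arm (Section 4); 30 baseline and 60 follow-up days (Section 4); 50% weekly alcohol use and Table 3 (Section 7). The 80% prompt response is an assumption borrowed from the payment threshold in Section 10. The documents give no daily-use distribution, no baseline to follow-up correlation and no alpha. Two-sided 0.05 is assumed.

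**1. Table 3 reproduced.** Two independent proportions, p1 = 0.50 and p2 = 0.50(1 - r), pooled variance under the null. For r = 0.5:

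- null SE = sqrt(2 × 0.375 × 0.625 / 60) = 0.0884
- alternative SE = sqrt((0.25 + 0.1875) / 60) = 0.0854
- power = Φ((0.25 - 1.96 × 0.0884) / 0.0854) = Φ(0.90) = 0.816

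For r = 0.2, 0.3, 0.4 and 0.5 this gives 0.194, 0.382, 0.611 and 0.816, against the stated 0.195, 0.381, 0.611 and 0.815. Table 3 is sound. It concerns the share of people who use alcohol and makes no use of the baseline data.

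**2. Simple change against adjustment, in theory.** With equal variances and correlation ρ, the variance per participant is 2σ²(1 - ρ) for change and σ²(1 - ρ²) for the adjusted comparison. The SE ratio is sqrt((1 + ρ)/2): 0.87 at ρ = 0.5, 0.92 at 0.68 and 0.98 at 0.91. For a power example, take σ = sqrt((0.25 + 0.2275)/2) = 0.489 and a difference of 0.15, only to set a scale. Power goes from 0.390 to 0.493 at ρ = 0.5, and from 0.758 to 0.800 at ρ = 0.8.

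**3. Zero baselines.** A person who drinks on a given day with probability p has no yes in Days 1-30 with probability (1 - 0.8p)^30: 0.79 for p = 0.01, 0.29 for p = 0.05, 0.14 for p = 0.08, and 1 for a non-drinker.

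**4. Simulation, 24 alcohol settings, 2,000 trials each (1,000 for the arm-level ratio).** Assumed: 50% weekly drinkers with daily probability Beta(0.8, 3.2) or Beta(1.4, 2.6); 0, 50 or 100% of the others drinking occasionally (0.01-0.08); between-period drift on the logit scale, SD 0.5 or 1.0, in both periods or in follow-up only; multiplicative 30% reduction. The share with zero baseline was 21-60%, and the baseline to follow-up correlation 0.68-0.91.

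| Analysis | Estimated reduction | 95% CI | Power |
|---|---|---|---|
| Adjusted (ANCOVA), % of control mean | median 29-30% | 30-60 points wide, coverage 0.96-0.98 | 0.38-0.93 |
| Simple change in proportion | | adjusted CI is 6-18% narrower | 0.30-0.84 |
| Per-person ratio, zero baselines omitted | mean 30-41 points | 57-132 points wide (1.6-2.5 times adjusted) | 0.18-0.58 |
| Arm-level ratio of ratios | median 29-31% | adjusted CI is 0.96-1.09 times as wide | adjusted differs by -3 to +5 points |

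Type I error for ANCOVA was 0.04-0.06. Its power gain over simple change was 10-16 points with drift in both periods and 2-9 with drift in follow-up only. With no effect its CI was 1-9% narrower, in line with step 2.

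The ratio overstates because dividing by a small noisy baseline inflates its mean. Where average behavior did not change between periods, the control arm still showed +2 to +33%. The arm difference then becomes 0.30 × 1.02 = 31 to 0.30 × 1.33 = 40 points, close to the simulated 30-41.

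**5. Other assumptions.** A wider grid (64 cells; 30% or 50% abstainers; four beta distributions; drift SD 0-1.5; reductions of 20-50%) gave:

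- zero baselines in 32-63% of participants;
- adjusted CI 10-25% narrower than simple change;
- power gain over simple change of 0-27 points, at most 16 in 56 of 64 cells; the largest cell rerun with 2,000 trials went from 60.1% to 81.8%;
- adjusted CI 0.82-1.40 times the arm-level ratio's.

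**6. Arm-by-period mixed model.** In 8 alcohol settings of 200 trials, a logistic model with a person-level intercept and period effect had type I error 0.03-0.08. Power was 0.385-0.875, against 0.385-0.955 for ANCOVA (difference -0.5 to +11.5 points). Its median odds ratio was 0.55-0.62 for a true 30% reduction. Read as a percentage reduction, that would be 38-45%. With a random intercept only and drift SD 0.5-1.0, type I error was 0.09-0.30 (300-trial runs).

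**7. Rarer behaviors.** With 8% or 15% regular users and 80-92% zero baselines, ANCOVA kept its type I error (0.04-0.06) and gained 0-13 points over simple change. Its percentage reduction had a CI 47-86 points wide and a median of 25-29% for a true 30%.

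**The case against.** The text leans away from the per-person ratio. The plan's example is a change in proportion and its method is a mixed model. A ratio gives one value per person, which leaves a person-level random effect nothing to separate from residual error. The mobility paragraph of Section 7 also plans random effects regression for binary outcomes. Modeling the repeated answers is therefore a natural reading. It is defined at zero baseline, and the adjusted analysis gains only modestly over it. An arm-level ratio of ratios is equally natural for the word relative, and there the gain is not consistent. The study is avowedly exploratory. All of this stands, and it limits the size of the point.

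It does not remove the point. The stated comparison is of change, no covariate or constraint is given, and the text does not choose among readings that return different numbers.

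Four stronger inferences are tempting, and the documents do not support them:

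- **The planned interval would be halved.** That holds only against the per-person ratio, which the plan does not specify.
- **The plan ignores baseline.** Change from baseline uses it; only a covariate or constraint is unstated.
- **The planned mixed model is invalid.** False positives rose only with a random intercept alone, a version the plan does not name.
- **Table 3 is wrong, or shares the scale of this analysis.** It reproduces, and it concerns the share of users. A weekly drinker who cuts down on drinking days but still drinks every week changes the share of yes-days and not Table 3's quantity.

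**Conclusion.** The point holds as an inexpensive improvement, with medium confidence. Effect scale, baseline covariate and equal-baseline constraint are all unstated, and adjusting for baseline improves on the simple change that the plan gives as its example. At a true 30% reduction with 60 per arm, the gain is about 6-18% in CI width and about 0-16 power points. Some plausible assumptions give 20 points or more. The per-person ratio should be excluded: it is undefined for about 21-63% of participants, biased upward, and roughly twice as imprecise.

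Every magnitude rests on assumed daily-use distributions, drift and response rates. The direction of the gain over simple change follows from the variance formulas. Its size at this trial cannot be fixed from the documents.

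**What to change.** Rewrite the analysis sentence of the change paragraph in Section 7 to say:

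- **Comparison.** For each yes/no behavior asked of everyone, compare arms on the Days 31-90 proportion of yes responses, adjusted for the Days 1-30 proportion. Use ANCOVA, or a mixed model on the repeated responses. The mixed model should have the baseline proportion as covariate, or cover both periods with arms constrained to equal baseline means and a person-level period effect as well as an intercept.
- **Zero baselines.** Include them, and do not use a per-person ratio.
- **Reporting.** Give the adjusted difference in proportions with 95% CI, and also as a percentage of the adjusted control-arm mean with 95% CI. Do not present the latter as Table 3's quantity. For rare behaviors let the absolute difference lead.
- **No follow-up responses.** Report the number by arm. Section 4 keeps participants who lose phones in all analyses, so retain them through the two-period mixed model or a sensitivity analysis. With an assumed 10% loss spread evenly over 90 days, this is about 120 × 0.10 × 30/90 = 4 people.
- **Separate treatment.** Condom use is asked only conditionally and items smoked is a count, so each needs its own stated analysis.

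The cost is one paragraph and a little programming. No extra data, visits or participants are needed. The small downside is the imprecise percentage reduction for rare behaviors.
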